The purpose of the study is, using study procedures duplicating in large part those of Garbutt et al (2012), to compare the benefits of 2 treatment arms—high-dose amoxicillin/clavulanate (2000 mg amoxicillin/125 mg po bid) vs regular-dose amoxicillin/clavulanate (875 mg amoxicillin/125 mg po bid)--at day 3 (primary endpoint) and day 10 (secondary endpoint), by reported degree of improvement (primary endpoint, as in Wald et al., 2009) and by SNOT-16 (secondary endpoint, but which was the primary endpoint in Garbutt et al, 2012). We will use amoxicillin/clavulanate, rather than amoxicillin alone, to be in accord with the IDSA 2012 guideline (IDSA, 2012). The duration will be 7 days in line with the IDSA guidelines. We will not have a pure placebo arm since 1) the IDSA guidelines recommend treatment; 2) clinical studies (Wald et al, 1986; Bucher et al., 2003) suggest that treating with the IDSA-recommended regular-dose amoxicillin/clavulanate is equivalent, or almost equivalent, to giving a placebo; 3) we will not exclude patients who we would not want to risk giving a true placebo; and 4) we know that, because of patients' continued belief in the efficacy of antibiotics, recruitment will be easily in a study with two treatment arms, rather than treatment and placebo arms. In addition, we will study whether the response to antibiotics can be predicted by the presence or not of penicillin-resistant S. pneumoniae in the nasopharynx.

Thus the study questions are: 1. Is high-dose amoxicillin/clavulanate superior to regulardose in improving the clinical symptoms of presumed sinusitis? 2. Does the higher dose result in increased incidence and/or severity of adverse effects, such as diarrhea? 3. Does the resistance pattern of S. pneumonia in nasopharyngeal cultures predict response to antibiotic treatment? The hypotheses are yes for #1, no for #2, and no for #3 (but with the expectation of insufficient power to answer question #3).

B. Study Design

Study type: randomized, double-blind clinical study with two active treatment arms

Location: AMC Internal Medicine and Pediatrics office in Latham, NY

Duration: 2 years; each participant will be in the study for 30 days.

Subjects:

Inclusion criteria

1. Adults age 18 and over. The study on children already indicates a benefit of high-dose amoxicillin-clavulanate over placebo. The restriction to adults eliminates the need for parental consent.

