6. Drop outs:

- a. The participant can exit the study at any time, if much sicker, by going to the emergency department
- b. The participant can request, at any time, treatment with open-label antibiotic, e.g. doxycycline or levofloxacin (recommended by the IDSA), at the discretion of the clinician in the office or on call.
- c. The participant will be formally given this option at the day 3 telephone call.
- 7. Participants will be asked additionally at day 10
 - a. To guess which treatment they took (to evaluate adequacy of blinding, although it is expected that patients who get better faster will assume they took the higher dose).
 - b. To indicate how many doses they took. We will not ask for the bottles to be returned (which would require an otherwise unnecessary office visit for the participants).
 - c. To indicate if they would take that particular medication again if prescribed.
- 8. Participants will be asked additionally at day 30 if, and to what extent, they had persistence, resolution, or recurrence of symptoms.

Measurements (bacteriological)

Nasal cultures (anterior) will be performed on every patient. The cultures will be processed at the Albany Medical Center microbiology laboratory to assess:

- 1. What pathogens are present?
- 2. If S. pneumonia, what is its level of penicillin resistance?
- 3. If S. aureus, is it methicillin resistant?

Endpoints

- 1. Primary endpoint: Major mprovement of subjective symptoms at day 3 (i.e., 48-72 hours after starting treatment), rated as "a lot better" or "no symptoms."
- 2. Secondary clinical endpoints:
 - a. At least mild improvement in subjective symptoms at day 3: percent in each group rating their condition as "a little better," "a lot better," or "no symptoms"
 - b. Improvement in SNOT-16 score at day 3. Garbutt et al. (2012) indicate that a minimally important difference is 0.5 (on a scale of 0-3), although they used an effect size of 0.25 for their study size determination (requiring a bigger sample size). We will compare the percent in each group with average improvement \geq 0.5
 - c. The same comparisons at days 10 and 30 (one month).
 - d. Comparisons of side effects—diarrhea and others mentioned by participants on scale of 0=none to 3=severe--at days 3 and 10.
 - e. Percent of who dropped out because of side effects or inefficacy (switched to alternative antibiotic or went to the ED).

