 - f. The impact of other clinical characteristics on the outcomes: age, sex, comorbidities, sinusitis category.

3. Secondary culture endpoints

- a. The proportion of participants with S. pneumoniae on NP culture and the proportion of these with moderate and high resistance to penicillin
- b. The proportion of participants with moderately or highly resistant S penumoniae versus the others who achieve the primary and secondary clinical end points

4. Other questions

- a. What percentages were treated without meeting IDSA criteria; were excluded; and refused to participate?
- b. How frequently did participants guess correctly which medication they were taking, and were their guesses associated with outcomes?
- c. How did the change in SNOT-16 score—and individual questions—correlate with holistic ratings of improvement?
- d. How many patients had MRSA, and did carriage of MRSA affect outcomes?

Sample size determination

1. For improvement in symptoms at day 3: Garbutt et al, 2012, has 34% symptom improvement in controls (placebo); if a clinically meaningful impact of high-dose amoxicillin-clavulanate is to increase the response rate to 50% (giving a NNT of 7), 146 patients in each group would be required to have an 80% power to detect this difference (if it exists), with alpha .05 (http://www.sealedenvelope.com/power/binary-superiority/).

- The statistical consultant calculates, with alpha .05 only one-sided (not inappropriate since we are interested only in improvement), the needed sample would be 120 in each group.
- 2. For change in SNOT score: Garbutt et al, 2012 calculated that 100 patients in each group were needed to detect a true difference of .25. To detect the "clinically meaningful difference" of .50, fewer would be needed.

We propose, therefore, to aim for 150 patients in each group, i.e. a total of at least 300 participants in Med-Ped over a 2 year period.

In our patient population of over 10,000, we see about 10 patients a week with presumed acute sinusitis during the non-summer months—a total of over 600 last year with a diagnostic code of acute sinusitis--so we expect no problem in reaching our recruitment goal.

Procedure

Prior to enrollment

- 1. All clinicians achieve up-to-date certification in research ethics. Only those who are certified will enroll patients.
- 2. PI trains all the nurses and clinicians to be able to explain the study to patients, collect study data, and obtain informed consent.

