- 3. Posters about the study are put in the waiting room and in the examining rooms.
- 4. The pharmacist prepares and numbers a set of medication bottles with either standard or high dose amoxicillin/clavulanate based on random number generation. Each bottle will include a label with dosing directions. A study allocation list will be kept by the pharmacist in a secure place in the office. The medication bottles and a log sheet to record medication #, patient name, and date will be kept in the locked medication room.

Enrollment

- 5. The nurse gives every patient with respiratory symptoms a SNOT-16 form to fill out and a handout about the sinusitis study (the same text that is posted in the waiting room and the examining rooms.) The nurse helps the patient to fill out the SNOT-16.
- 6. The clinician then assesses every patient with respiratory symptoms for suitability for the study, i.e., determines if the patient has acute sinusitis and is eligible for study, using the standard diagnostic criteria and considering the inclusion and exclusion criteria (marking them on the Data Collection Form).
- 7. The clinician indicates the disposition of each patient treated for acute sinusitis: meets criteria for inclusion, but not asked to participate (e.g., lack of time); treated even though not meeting IDSA criteria for acute sinusitis; presence of exclusion criterion; meeting all criteria but declined to participate; or entered into the study.
- 8. The clinician or nurse explains the study based on the Enrollment Script; the clinician obtains informed consent; and the clinician or nurse makes a copy of the consent form to give to the patient.
- 9. The clinician or the nurse obtains a nasal culture. If the patient prefers, he or she can insert the swab (under supervision to make sure it goes to mid nasal passage).
- 10. The clinician or nurse obtains the already-randomized medication bottle, writes the patient's name and date on the log sheet or (preferred) attaches a patient sticker, and writes the patient's number on the informed consent and on the culturette. The clinician gives the bottle of medication to the patient.

- 11. The patient is told that one tab has regular amoxicillin with clavulanate, the other tab has either a different formulation of amoxicillin with clavulanate or else an inactive ingredient (so that patients are not surprised if the pills look slightly different).

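### The aim, study question 3 and endpoint 3a are stated for nasopharyngeal cultures, but the only specimen described is a nasal swab

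*Combined protocol and SAP*

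**What the plan says.** Under Purpose of Current Study, the aim reads "we will study whether the response to antibiotics can be predicted by the presence or not of penicillin-resistant S. pneumoniae in the nasopharynx". Study question 3, in the next paragraph, asks "Does the resistance pattern of S. pneumonia in nasopharyngeal cultures predict response to antibiotic treatment". The hypothesised answer is no, with the qualification "but with the expectation of insufficient power to answer question #3".

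Under Endpoints, secondary culture endpoint 3a is "The proportion of participants with S. pneumoniae on NP culture and the proportion of these with moderate and high resistance to penicillin". Endpoint 3b compares the proportion of participants with "moderately or highly resistant S penumoniae versus the others who achieve the primary and secondary clinical end points".

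The sampling itself is described in two places. Measurements (bacteriological) says "Nasal cultures (anterior) will be performed on every patient". Procedure, Enrollment, step 9 says "The clinician or the nurse obtains a nasal culture", and adds "If the patient prefers, he or she can insert the swab (under supervision to make sure it goes to mid nasal passage".

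**The concern.** The endpoint names one anatomical site and the procedure samples another. If both are followed literally, no culture exists from which to report endpoint 3a. More probably, nasal-swab results would be reported under a nasopharyngeal label.

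The label matters because the Background treats specimen sites as different things. It contrasts sinus aspiration, endoscopically guided middle meatal culture and nasopharyngeal culture, and discusses what each can tell the clinician. It also cites a culture-response study based on nasopharyngeal secretions. A reader who sets this trial's result beside that literature would take it to concern the same site.

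Question 3 is one of only three study questions, and its expected answer is no. A null result attributed to the wrong site could be read as confirming a hypothesis about nasopharyngeal colonization that the trial did not examine.

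**Working it through.** The main point needs no arithmetic, and the plan gives no figure of its own for question 3 or endpoints 3a and 3b. The check is a comparison of the places that name a site.

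| Place | Site named |
|---|---|
| Purpose of Current Study, aim | nasopharynx |
| Purpose of Current Study, question 3 | nasopharyngeal cultures |
| Endpoints, 3a | NP culture |
| Endpoints, 3b | none stated |
| Measurements (bacteriological) | anterior nasal |
| Procedure, Enrollment, step 9 | nasal; mid nasal passage if self-inserted |

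Three statements of the target are nasopharyngeal. Both descriptions of sampling are nasal, and they also differ from each other on depth. No sentence in the available text bridges the two.

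On what is collected: the laboratory is to identify pathogens for every patient and the penicillin resistance level of any S. pneumoniae. Participants can therefore be classed as having resistant S. pneumoniae, susceptible S. pneumoniae or none, without further data. The defect lies in the label, not in the collection.

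A secondary point concerns endpoint 3b. If its comparison group is everyone without resistant S. pneumoniae, it pools susceptible carriers with non-carriers. An illustration shows what that contrast measures.

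Inputs: 300 participants (Sample size determination). Carriage of 32.7% is the meta-analysis culture rate in the Background, which gives no specimen site, so applying it to a nasal swab is an assumption. Resistance of 10% is also assumed; the Background reports local penicillin sensitivity above 90% but doubts that this reflects the community. Response rates of 34% and 50% are borrowed from the sample size section and assigned to groups by assumption.

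- Carriers: 300 × 0.327 = 98.1. Resistant: 98.1 × 0.10 = 9.8. Susceptible: 88.3. Non-carriers: 201.9. All except the resistant: 290.2.
- Suppose resistant carriers respond at 34%, susceptible carriers at 50% and non-carriers at 34%. The pooled group responds at (88.3 × 0.50 + 201.9 × 0.34) / 290.2 = 38.9%. The 3b contrast is 4.9 points, although resistant and susceptible carriers differ by 16.
- With non-carriers at 60% instead, the pooled group responds at (88.3 × 0.50 + 201.9 × 0.60) / 290.2 = 57.0%, and the contrast is 23.0 points.
- With carriage at 10% and resistance at 10%, the same two cases give 1.5 and 25.1 points.

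The pooled contrast thus moves with the response of non-carriers even when the effect of resistance is fixed. As for precision, 5 responders among 10 resistant participants has a 95% Wilson interval of 23.7% to 76.3%, so any such table can only be descriptive.

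**The case against.** The strongest reply is that this is loose vocabulary. The same swab is meant throughout, every patient has one, and the pathogen and resistance results are recorded. This stands as to data: nothing is lost. It does not stand as to meaning, because the protocol itself distinguishes specimen sites when it argues what a culture can show.

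On endpoint 3b the reply is stronger. The aim is framed as presence or absence of resistant S. pneumoniae, and the study questions are introduced as following from it. Read together, endpoint 3b answers the aim. A reader might infer that it is an invalid comparison; the documents do not support that. It is a legitimate predictive contrast that does not isolate resistance among carriers. Its comparison group is also undefined: after 3a it could mean the other S. pneumoniae carriers, in which case there is no pooling.

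Nor does the cited culture-response study make separate groups necessary. It concerned any pathogen and whether antibiotics were given, whereas both arms here receive an antibiotic.

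A reader might further infer that the nasal swab will miss carriers, that question 3 needs a new specimen, or that the culture work is wasted. The documents give no nasal-versus-nasopharyngeal yield, so the first cannot be argued from them. The second does not follow, since rewording is enough. The third ignores that the same swab also serves general pathogen identification and the MRSA question.

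Finally, low power for question 3 is already conceded, so small resistant counts are not a new criticism.

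**Conclusion.** The plan is wrong as written on the specimen site, and the matter is minor. The aim, question 3 and endpoint 3a refer to the nasopharynx, while the only specimen described in the available text is nasal. Until this is reconciled, endpoint 3a has no matching specimen and conclusions on question 3 would carry the wrong site.

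The conclusion rests on the text alone and on no assumed rate. It does assume that no omitted page describes a nasopharyngeal swab or a stated substitution. The comparison group in endpoint 3b calls for a clarification only. The primary endpoint, the 150 per group and the conceded lack of power for question 3 are untouched.

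**What to change.** Reconcile the specimen site across Purpose of Current Study, Measurements (bacteriological), Endpoints and Enrollment step 9, including the difference between anterior and mid nasal sampling. One way that leaves sampling as it is: restate the aim, question 3 and endpoints 3a and 3b as S. pneumoniae on nasal culture, and limit conclusions to nasal carriage.

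As an optional supplement from data already collected, keep the presence-or-absence contrast in 3b and say in one line that its comparison group is all remaining participants. Then show response descriptively for resistant S. pneumoniae, susceptible S. pneumoniae and no S. pneumoniae, with 95% confidence intervals. Overall figures suffice; a split by arm is not needed.

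The cost is protocol wording and, if wanted, one table, with no extra specimen or visit. The downside is a narrower claim, and power does not improve.

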2003). One reason for the questionable value of amoxicillin/clavulanate may be that clavulanate has been shown (Dinis et al, 2000) to have uneven penetration into sinus tissue (and would likely, therefore, to have at least as uneven penetration into sinus fluid). Moreover, the impact of adding clavulanate is diminished, as acknowledged by the IDSA, by the presence, in a variable proportion of patients, of penicillin-resistant S. pneumoniae (as well as methicillin-resistant S. aureus); it is for this reason that the IDSA recommends high-dose amoxicillin/clavulanate when the rate of penicillin-resistant S pneumoniae exceeds 10%. Indeed, the superior effectiveness of high dose was suggested by a small retrospective study in which the number of resistant S. pneumoniae in nasopharygeal swabs was reduced from 8 cases before treatment to 5 cases after treatment with 1.5 grams per day of amoxicillin with clavulanate but from 8 cases to only 1 case after treatment with 4.0 grams day of amoxicillin with clavulanate (Brook et al., 2005).

Third, studies could have been falsely negative if the methods used to measure the effect underestimated it. Garbutt et al (2012) used the mean response to the 16 questions of the SNOT-16 as the primary outcome. Is it possible that the responses to the truly meaningful questions (e.g. fatigue) were diluted by responses to questions that are less important to the patient or do not change very fast (e.g. runny nose) or are not much affected by antibiotics (e.g. sneezing)? In support of its validity as a measure of treatment effect, however, the SNOT-16 was validated by another group (Quadri et al, 2013), and the question on subjective improvement also showed no significant difference at day 3 (37% of amoxicillin group vs 34% of placebo group reported that symptoms were a lot better or absent), although at day 7 there was a significant increase in subjective improvement in the antibiotic group (74% vs 56%, p=.02).

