Note that, unlike the IDSA guidelines, (2012) we do not plan automatically to treat with high-dose amoxicillin/clavunate all patients >65 or those who were hospitalized recently but not treated with antibiotics.

- 8. Suspicion of MRSA.
- 9. Drug warnings
 - a. Chronic kidney disease with estimated GFR < 30;
 - b. Hepatic impairment (not including isolated transaminase elevation <2 times normal);
 - c. Current mononucleosis (because of amoxicillin-induced rash);
 - d. History of antibiotic-associated colitis.
- 10. Need to hospitalize because of severity of infection, respiratory distress, or vulnerability of patient.

Treatment arms

- 1. Amoxicillin/clavulanate 1000/62.5 ER 2 tabs po bid for 7 days. (total pill burden 4 per day)
- 2. Amoxicillin/clavulanate 875/125 tabs 1 tab + 1 placebo tab po bid for 7 days (total pill burden 4 per day).

The duration of 7 days is in accordance with IDSA guidelines.

Both groups would be advised: 1) to instill saline into each nostril at least 2 times a day (1/4 tsp salt dissolved in 4 oz of distilled or boiled water, 1 teaspoonful administered into each nostril by sniffing, by syringe, or by Neti-pot; 2) to take acetaminophen for discomfort (not to exceed a total daily dose of 3 grams, or 2 grams if the patient drinks ETOH).

The pharmacist would prepare the medication bottles and randomize them (i.e., number the two sets of medication bottles as determined by a random number generator and keep the list of correlations between bottle number and actual contents).

Measurements (clinical)

- 1. Diagnostic criteria for acute sinusitis (as listed above): clinician to record these (including duration of illness and the category of acute sinusitis)
- 2. Initial additional data collection by nurse or clinician: previous side effects with antibiotics, antibiotics within past month, hospitalization in past 5 days, comorbidities (e.g., diabetes, heart disease, and lung disease)
- 3. Sinonasal Outcome Test-16 (SNOT-16) at days 0, 3, 10, and 30 (for validation of the form, see Garbutt et al, 2011, and Quadri et al, 2013).
- 4. Patients' summary assessment of their condition at days 3, 10, and 30: a lot worse, a little worse, the same, a little better, a lot better, no symptoms (as used by Garbutt et al, 2012).
- 5. Side effects at days 3 and 10
 - a. Diarrhea: none, mild, moderate, severe
 - b. Allergic reaction: rash without itching, rash with itching or hives
 - c. Other: abdominal pain, vaginal discharge and itching, other

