- 2. Research assistant (coordinator if possible) (if the resident on medical home rotation or a work-study student is not a feasible option)
 - a. Telephoning patients: 1 hour per patient x 300 patients @ \$20 per hour = \$6,000
 - b. Entering data: 100 hours a \$20 per hour = \$2,000.
- 3. Statistician: 20 hours @ \$100 per hour = \$2,000.
- 4. Cultures: estimate of \$100 per culture= \$30,000.
- 5. Duplication of forms: 600 @ 10 cents = \$60.
- 6. Study binders: 300 @ 50 cents = \$150.
- 7. Overall cost: \$44,550.
- 8. Funds will come from the AMC Med-Ped Research Fund, derived from private contributions and held by the Albany Medical Center Foundation, at the discretion of the Medicine-Pediatrics Division Head (currently [name]).

C. Subject Population

Source of participants: the patients of AMC Internal Medicine and Pediatrics, [name], who present with respiratory symptoms.

Total number of participants to be enrolled: 300.

Characteristics of population: adults, with no special populations (see Inclusion and Exclusion criteria above).

D. Data Analysis

See the Data Collection Sheet for a listing of the data that will be collected.

The Data Collection Sheets will be stored in a locked drawer in the PI's office.

The data will be entered by the research assistant (or Med-Ped residents or medical students doing work-study) into an Excel data base stored on a password-protected computer in the PI's office.

The Excel data base will be stripped of patient identifiers and transferred to SPSS by the statistical consultant, [name], who will, in turn, perform the analyses.

The primary analysis will be a simple chi-square analysis, with an alpha of .05%, of the difference in the primary endpoint (the proportion of participants who are "a lot better" or "no symptoms" at 3 days).

The analyses of the secondary outcomes (listed above) will depend on the nature of the data and be determined by the statistician.

E Risks

Risks of treatment

The side effects of treatment with amoxicillin/clavunate include:

- 1. Allergic reaction, usually minor, sometimes severe enough to send to the ED, very rarely resulting in death. Wikipedia's entry on anaphylaxis suggests death in about 1 out of 50,000 courses of penicillin.

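### The SNOT-16 endpoint compares percentages improving by 0.5 or more, but its size support is for a difference in score; a baseline-adjusted mean comparison would recover power below 0.5

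*Combined protocol and SAP*

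**What the plan says.** Endpoint 2b (B. Study Design, Endpoints) is introduced as "Improvement in SNOT-16 score at day 3". The one comparison it names is of proportions: "We will compare the percent in each group with average improvement" of 0.5 or more. It takes 0.5 from the cited placebo-controlled amoxicillin trial as the minimally important difference on a 0-3 scale, and adds of that trial's investigators: "although they used an effect size of 0.25 for their study size determination". Endpoint 2c repeats the comparison at days 10 and 30.

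Sample size determination, item 2, says the same investigators "calculated that 100 patients in each group were needed to detect a true difference of .25". For a difference "of .50, fewer would be needed". The background, before Purpose of Current Study, says that trial "used the mean response to the 16 questions of the SNOT-16 as the primary outcome".

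The baseline score is available: Measurements (clinical), item 3, lists the "Sinonasal Outcome Test-16 (SNOT-16) at days 0, 3, 10, and 30". D. Data Analysis specifies a chi-square test for the primary endpoint and says the secondary analyses "will depend on the nature of the data and be determined by the statistician".

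**The concern.** The size support and the named analysis are on different scales. The 100 per group is for a difference in score, in a trial whose outcome was a mean. Endpoint 2b turns each patient's change into yes or no at 0.5 and compares percentages. The figure 0.5 also has two roles: a per-patient cut-off in 2b, and a between-group difference in item 2. A difference of 0.25 in means is not a difference of 0.25 in anything that 2b compares.

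Dichotomising discards information. It costs little when the true difference is large, but a smaller shift could be missed by the responder comparison when a comparison of means on the same data would probably detect it. The day-0 score is used only to form the change. No between-arm comparison of means, adjusted or not, is prespecified.

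**Working it through.** **Inputs from the documents.** 100 per group for a difference of 0.25 (sample size, item 2); cut-off 0.5 (endpoint 2b); 150 per arm (sample size).

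**Assumptions, because the documents are silent.** Two-sided .05; normally distributed change with equal SD in both arms; control-arm mean improvement between 0 and 1.0; correlation of baseline with follow-up score 0.3 to 0.7.

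**Step 1: the plan's own figure.** The 100 per group cannot be reproduced without its SD, alpha and power, so I solved for the SD it implies:

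SD = √[100 × 0.25² / (2 × (z_α + z_power)²)]

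- Two-sided .05, 80% power: √[6.25 / (2 × (1.960 + 0.842)²)] = 0.631
- Two-sided .05, 90% power: √[6.25 / (2 × (1.960 + 1.282)²)] = 0.545
- One-sided .05, 80% power: √[6.25 / (2 × (1.645 + 0.842)²)] = 0.711

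I first take this as the SD of change.

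**Step 2: means at a difference of 0.25, 150 per arm.** The noncentrality is 0.25 / (0.631 × √(2/150)) = 3.43 on 298 df, giving power 92.8%. With SD 0.545 it is 97.7%.

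**Step 3: the same shift as percentages.** The responder rate in an arm with mean improvement m is P(change ≥ 0.5) = Φ((m − 0.5)/SD). I used the pooled two-proportion z test. For a control mean of 0.375 and SD 0.631 the rates are Φ(−0.198) = 42.1% and Φ(0.198) = 57.9%. The standard error is 0.0577 under the null and 0.0570 under the alternative. Power is Φ((0.157 − 1.960 × 0.0577)/0.0570) = 77.9%.

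| Control mean improvement (SD 0.631) | Responders, control v high dose | Power at 150 per arm |
|---|---|---|
| 0 | 21.4% v 34.6% | 72.3% |
| 0.375 | 42.1% v 57.9% | 77.9% |
| 1.0 | 78.6% v 88.3% | 61.7% |

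With SD 0.545 the responder range is 68.3%-88.5%. At the cited 100 per group and SD 0.631, it is 45%-60%. For 80% power at 0.25 (SD 0.631), the responder comparison needs 158-231 per arm and the comparison of means needs 101.

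**Step 4: baseline adjustment.** With equal variances at baseline and follow-up, residual SD = SD of change × √((1 + r)/2). For SD of change 0.631 the ANCOVA power at 0.25 is 98.9% (r = 0.3), 97.7% (r = 0.5) and 96.0% (r = 0.7). A simulation (4,000 runs, r = 0.5, control mean 0.5) gave 0.927 for mean change, 0.780 for responders and 0.976 for ANCOVA.

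**Step 5: if 0.631 is the SD of the score.** Then SD of change = 0.631 × √(2(1 − r)) and residual SD = 0.631 × √(1 − r²).

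| r | SD of change | ANCOVA power | Responder power |
|---|---|---|---|
| 0.3 | 0.747 | 95% | 52%-64% |
| 0.5 | 0.631 | 98% | 62%-78% |
| 0.7 | 0.489 | 99.8% | 72%-94% |

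**Step 6: a difference of 0.50.** At 150 per arm the lowest responder power is 98.1% (SD 0.631) or 98.6% (SD 0.545), both at control mean 1.0. With SD 0.631, 41-73 per arm give 80%. Item 2's remark that fewer are needed for .50 therefore holds even for the responder comparison.

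**The case against.** The strongest reply is that the protocol names 0.5 as the difference that matters, and at 0.50 the responder comparison is well powered. A clinically interpretable cut-off is then a deliberate choice, and insensitivity to smaller differences is its price. This stands as far as 0.50 goes. But the protocol nowhere says that a group difference below 0.5 in mean score is unimportant, and its only SNOT-16 sample size is for 0.25.

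Second, the 150 per arm comes from the primary endpoint (146 per group), and a secondary endpoint needs no sizing of its own. That is right: the mismatch leads to no wrong sample size.

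Third, D. Data Analysis leaves secondary methods open, so a mean analysis is not excluded. True, but 2b already names the responder comparison, and a method chosen according to the data is not prespecified. A mean comparison added later would look post hoc.

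Fourth, the size of the loss rests on assumptions.

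- The 62% end needs a control mean improvement of 1.0, which looks high for day 3. With control means of 0 to 0.5 the responder power is 72%-78% (SD 0.631) or 82%-89% (SD 0.545).
- One-sided sizing of the cited figure (SD 0.711) lowers mean power at 0.25 to 86%, against 55%-68% for responders.
- Scores are bounded at 0 and may gather there by day 30, so the normal-shift powers are least secure at that visit.

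These points change the size of the gap. They do not reverse its direction, which also held when only 25%-50% of patients were assumed to benefit.

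**Conclusion.** The concern holds. That the named analysis and its size support are on different scales can be read directly from the documents and needs no assumption. For a true difference of 0.25 at 150 per arm, the responder comparison gives up about 15 to 31 percentage points of power against a comparison of means (93% v 62%-78%, SD 0.631). Under one-sided sizing the gap is 86% v 55%-68%; with SD 0.545 it is 98% v 68%-88%. ANCOVA adds a few points more. At 0.50 there is almost nothing to recover. All these sizes depend on an SD inferred from another trial's sample size, an assumed control improvement, an assumed correlation and a normal shift. The matter is a gain in precision on a secondary endpoint and does not touch the primary analysis. It is worth changing because the gain needs no extra data.

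**What to change.** 1. In endpoints 2b and 2c, make the main SNOT-16 analysis at days 3, 10 and 30 an ANCOVA of mean score on arm with day-0 SNOT-16 as covariate. Report the adjusted mean difference with its 95% CI.
2. Keep the percentage improving by 0.5 or more as a supportive responder analysis.
3. In sample size item 2, state that 100 per group applies to the comparison of means only, and give the SD, alpha and power assumed.
4. Leave the primary chi-square as it is. A baseline-adjusted version of the primary would be optional and supportive only.

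The cost is a change of wording. The day-0 and follow-up scores are already collected; no visits, patients or measurements are added.
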